### **2.1 Primary Hypotheses**

Hypothesis 1A: As compared with clopidogrel, treatment with ticagrelor will result in significantly reduced risk of MACE, i.e. non-fatal myocardial infarction, non-fatal stroke, CV death, severe recurrent ischemia, and stent thrombosis if not captured in other events, in patients with reduced function *CYP2C19* allele(s) (as identified retrospectively by the ABI TaqMan platform) who undergo PCI. This hypothesis will be tested with a two-sided test at a Type I error rate of 0.05.

Hypothesis 1B: In patients undergoing PCI who are wild type with respect to *CYP2C19* (by TaqMan), and who receive clopidogrel, prospective knowledge of their genotype (according to the Spartan® platform results) does not alter the risk of MACE. This hypothesis will be tested formally only if the null hypothesis for Hypothesis 1A is rejected.

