### C. Statistical Calculations

*Likelihood Method for Real Time Estimation of Treatment Effect and Event Rates:* At any point in time during the TAILOR-PCI trial, there are two sources of data on the treatment effect: 1) data from subjects with 1 complete year of follow-up and TaqMan processing completed (“complete” data), and 2) the data on those with less than 1 year of follow-up or without TaqMan processing, half of whom have been genotyped using SPARTAN (“incomplete”). The *complete* subjects have complete endpoint and genotype data, while the *incomplete* subjects have incomplete endpoint and incomplete genotype data. Nevertheless, both sets of data have information on the treatment effect, and this information can be quantified. The analysis of the subjects who have undergone TaqMan is straightforward; a good approximation is a binomial comparison between the two LOF groups, in terms of their one year event rate. To recover the information in the prospectively randomized subjects who have not had TaqMan analysis complete, we propose the following simplified yet highly accurate approach.

There are 3 groups: 1) prospectively genotyped, loss of function carriers (PG-LOF) who are given ticagrelor, 2) prospectively genotyped, wild type subjects (PG-WT) who are given clopidogrel and 3) conventional therapy (CT) who are given clopidogrel. Let us simplify the primary endpoint to a binary outcome  $X$  (yes or no) with a probability that depends on: genotype( $G$ ), treatment( $Rx$ ), and follow-up time. Specifically, we assume that, for a subject with genotype  $G$ , treatment  $Rx$ , and observed for  $t$  years, the probability of an event is:

$$\begin{aligned} \Pr\{X = 1|G, Rx, t\} &= \lambda_{G,Rx} * \frac{[1 - S(t)]}{[1 - S(1)]} \\ &= w(t) * \lambda_{G,Rx} \end{aligned}$$

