where  $S(\cdot)$  is the overall underlying survival curve for freedom from events,  $t$  is time in years. Note that if the subject experiences the primary endpoint, the value of  $t$  is not tied to the event time itself, but rather reflects the visit date (roughly 1 month, 6 months, or one year) representing the effective amount of follow-up for that patient (time from randomization to last follow-up date). To calculate  $S(\cdot)$ , we simply use the Kaplan-Meier curve for the entire study population. This fraction therefore represents the fraction of a “risk year” to which that subject was exposed, i.e. it is an estimate of the proportion of events occurring within a year that have occurred at the follow-up time for the specific individual. Note that we consider  $w(t)$  to be a fixed quantity, rather than a parameter, though technically it is estimated from the entire data set.

We further assume that the event rates (1-year probabilities) are:

$$\lambda_{WT,CL} = \lambda_1$$

$$\lambda_{LOF,TIC} = \lambda_2$$

$$\lambda_{LOF,CL} = \lambda_3$$

We also assume that the rate of wild type subjects exposed to clopidogrel ( $\lambda_1$ ) is the same whether they are in the conventional therapy or the prospective genotyping group. This is a fundamental assumption, but one which will also be ultimately tested.

The treatment effect of interest can be expressed as  $\lambda_2/\lambda_3$ , that is, the relative risk associated with

ticagrelor in LOF subjects. The trial's primary hypothesis is that this number is substantially less than 1.0. (Relative risk reduction is 1 minus this quantity). Finally, let  $\alpha$  be the population prevalence of the LOF genotype in the population being randomized. We can now define the likelihood contributions of members of each of the three groups of "incomplete" subjects.

For those in the PG-WT and PG-LOF groups, the likelihood contributions, respectively, are:

$$L(\lambda_1|X, t) = [\lambda_1 * w(t)]^X * [1 - \lambda_1 * w(t)]^{(1-X)}$$

$$L(\lambda_2|X, t) = [\lambda_2 * w(t)]^X * [1 - \lambda_2 * w(t)]^{(1-X)}$$

For those in the CT group, the likelihood contribution is a weighted average of the likelihood contributions that would be obtained under (WT, CLOP) and (LOF, CLOP) conditions, weighted by the probability of each genotype, namely:

$$L(\lambda_1, \lambda_3, \alpha|X, t) = (1 - \alpha) * L_1(X, t) + \alpha * L_3(X, t)$$

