where  $L_1$  and  $L_3$  have the obvious definitions parallel to the 'known-genotype' likelihoods spelled out above. If this were the only data available, then the 4 parameters ( $\lambda_1, \lambda_2, \lambda_3, \alpha$ ) would not be identifiable, i.e.  $\alpha$  and  $\lambda_3$  would be completely confounded. However, we have one further piece of data: the numbers of LOF and WT subjects in the PG group. These numbers can be put into a binomial likelihood with  $\alpha$  as the only parameter. The random variable corresponding to this proportion is statistically independent (at least uncorrelated), with all the other likelihood pieces. Therefore, the overall likelihood is the product of all the conditional likelihood pieces for the members of the 3 groups, along with this binomial likelihood for the prevalence of LOF. This serves to identify both  $\alpha$  and therefore  $\lambda_3$  as parameters. Thus in this complete likelihood, all 4 parameters are identified. Thus, the *incomplete* data provides a likelihood that *is* informative about the treatment effect (subject to the null hypothesis assumption regarding the effect of knowledge of genotype on the WT/CLOP response). The likelihood from these data can be combined with the simple TaqMan binomial data to derive a combined likelihood which incorporates both pieces of information.

*Estimation of Information Time:* We can also estimate the proportion of total study information contained in the current data. First, we estimate the expected information at the end of the trial as the

inverse of the expected square of the standard error of the hazard ratio of interest. Our expected power of 85.8% implies that our expected z-score at the end of the trial is 3.031. Given a minimum detectable effect size of 0.50, the expected standard error at study end is 0.2287 ( $\log(0.5)/3.031$ ). Thus the expected final information is 19.1. Second, the available information in the current data is calculated using a profile likelihood approach to estimate the standard error of the current estimate of the treatment effect. The ratio of the current information to the expected final information is the estimated information time.

*Calculation of conditional power:* Conditional power is a function of the current effect estimate z-score and information time. Its formula is:

$$CP(t, Z_t) = 1 - \Phi\left[\frac{\Phi^{-1}(0.975) - Z_t \sqrt{t}}{\sqrt{(1-t)}}\right] - (\Phi^{-1}(0.975) + \Phi^{-1}(P_0)) * \sqrt{(1-t)}$$

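### Appendix C's interim likelihood ties the wild-type event rate across arms and has no term for TaqMan-complete wild-type outcomes, which would add information and let the assumption be checked at each look

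*Combined protocol and SAP*

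**What the plan says.** Appendix C (Statistical Calculations) divides patients into complete (one year of follow-up and TaqMan done) and incomplete.

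- **Complete patients.** The only outcome analysis described is in carriers of a loss-of-function (LOF) allele: "a good approximation is a binomial comparison between the two LOF groups, in terms of their one year event rate".
- **Incomplete patients.** Those in the genotyping arm enter as known wild type or known LOF. Those in the conventional arm enter as a mixture of the two.
- **LOF prevalence.** It is identified from "the numbers of LOF and WT subjects in the PG group".
- **The link between arms.** The wild-type clopidogrel rate "is the same whether they are in the conventional therapy or the prospective genotyping group". Appendix C comments: "This is a fundamental assumption, but one which will also be ultimately tested". It later says that the incomplete data are informative "subject to the null hypothesis assumption regarding the effect of knowledge of genotype on the WT/CLOP response".
- **Combination.** "The likelihood from these data can be combined with the simple TaqMan binomial data to derive a combined likelihood".

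Section 2.1 states the same equality as Hypothesis 1B, that knowledge of genotype "does not alter the risk of MACE. This hypothesis will be tested formally only if the null hypothesis for Hypothesis 1A is rejected". Section 15.8 feeds the resulting estimate and standard error into information time, conditional power and the efficacy looks.

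**The concern.** An untyped conventional-arm patient is an unknown mixture. The LOF rate in that group is recovered by subtracting a wild-type rate, and under the plan that rate is learned from incomplete wild-type patients in the other arm. If the two wild-type rates differ, the difference passes into the estimated LOF rate on clopidogrel, and so into the interim relative risk, z and conditional power.

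The trial is open label, so equality cannot be taken for granted. The promised test may also come too late to help: 1B is formally tested only if 1A is rejected, so after a futility stop it need not be tested at all. Meanwhile, TaqMan-complete wild-type patients in the conventional arm estimate the needed rate directly, within the same arm, yet no likelihood term uses them.

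**Working it through.** **The plan's own figure.** With "Our expected power of 85.8% implies that our expected z-score at the end of the trial is 3.031": z = 1.960 + 1.071 = 3.031; SE = ln 2 / 3.031 = 0.2287; information = 1/0.2287² = 19.1. This agrees with Appendix C.

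**Inputs from the documents.**
- Section 15.2.2 gives an overall LOF event rate of 4.5% and a ratio of 0.50. Hence λ3 × (1 + 0.5)/2 = 0.045, so λ3 = 6.0% (clopidogrel) and λ2 = 3.0% (ticagrelor).
- LOF prevalence α: Table 4 has 1,413 Korean and 3,742 North American patients at N = 5,155. Adding 115 at 20% Korean gives 1,436 and 3,834. Then (0.59 × 1,436 + 0.28 × 3,834)/5,270 = 36.4%.

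**Assumptions not in the documents.** Wild-type rate λ1 = 3.6%; w = 0.7 for every incomplete patient; the complete/incomplete split at each look; and the ratio r of the genotyping-arm to the conventional-arm wild-type rate.

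**Mechanism.** The conventional-arm mixture has rate 0.636 × 0.036 + 0.364 × 0.060 = 0.0447. The plan subtracts 0.636 × r × 0.036 and divides by 0.364. From the incomplete data alone:
- r = 0.80: (0.0447 − 0.0183)/0.364 = 7.3%
- r = 1.25: (0.0447 − 0.0286)/0.364 = 4.4%

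The true value is 6.0%. Complete LOF data dilute the error.

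**How much rests on the incomplete data.** At 1,300 + 1,300 there are 650 × 0.364 = 236.6 complete LOF patients per arm. The variance of log(λ2/λ3) from these alone is 0.97/(236.6 × 0.03) + 0.94/(236.6 × 0.06) = 0.203, or information 4.93. The plan's combined likelihood gives 7.41, so about a third comes from incomplete patients. Information time is 7.41/19.1 = 0.39.

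**Bias of the plan's estimate** (maximum of the expected combined likelihood, true relative risk 0.50):

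| Complete + incomplete | r = 0.80 | r = 1.00 | r = 1.25 |
|---|---|---|---|
| 1,300 + 1,300 | 0.480 (z −2.01) | 0.500 (z −1.89) | 0.522 (z −1.76) |
| 1,000 + 2,300 | 0.464 (z −2.21) | 0.500 (z −1.95) | 0.542 (z −1.69) |
| 500 + 2,500 | 0.447 | 0.500 | 0.570 |

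The arm-specific model keeps 0.500.

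**Information for log(λ2/λ3)** (inverse Hessian of the same likelihoods):

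| Complete + incomplete | Plan | Common rate, wild-type data added | Arm-specific |
|---|---|---|---|
| 1,300 + 1,300 | 7.41 | 7.58 | 7.47 |
| 2,300 + 1,600 | 11.82 | 12.04 | 11.95 |
| 1,000 + 2,300 | 7.95 | 8.23 | about 3% below plan |
| 500 + 2,500 | | | 0.863 × plan |
| 300 + 3,000 | | | 0.684 × plan |

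The gain from adding the data under a common rate is 7.58/7.41 = 1.023, 12.04/11.82 = 1.019 and 8.23/7.95 = 1.035. The arm-specific model replaces the genotyping arm's incomplete wild-type events, proportional to w × incomplete N, with the conventional arm's complete ones, proportional to complete N. Break-even is therefore near complete N = w × incomplete N.

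**The case against.** The plan discloses the assumption, repeats it as a condition and ties it to 1B. Both wild-type groups are assigned the same drug, endpoints are adjudicated blind (Sections 12.3 and 14.3), and Section 15.5 expects the 1B null to hold. The ratios 0.80 and 1.25 are hypothetical. At 1,300 + 1,300 the three z values give conditional power of about 0.93, 0.91 and 0.90, against a futility threshold of 0.858 × (1 − 0.39) = 0.52, and none is near the efficacy value of 3.291. Futility is only a consideration for the DSMB, and Section 15.8 neither recommends nor anticipates stopping for efficacy. All of this stands, and it keeps the point minor.

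It is not always harmless, however. At 500 + 2,500 with a true relative risk of 1.0 (4.5% in both LOF groups), r = 0.80 gives conditional power 0.62 against a threshold of 0.56. With equal wild-type rates it is 0.58 against 0.60, so the futility reading changes. That case lies before the 40% efficacy look, but Section 15.8 applies futility at DSMB reviews.

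A reader might infer that arm-specific rates could simply replace the common rate at no cost. The documents do not support that. Section 5 places TaqMan typing at an unspecified time after one year, Section 15.9.1 refers to results in batches, and Appendix C counts anyone untyped as incomplete. Splits with few complete patients are therefore possible, and there the arm-specific model loses information. Even where it exceeds the plan, the gain comes from the added data: keeping the common rate with the same data does better still (7.58 against 7.47).

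A reader might also infer that the plan throws the wild-type data away. It does not say so; the term is simply absent, and the method describes itself as simplified.

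**Conclusion.** The point holds as a minor improvement to interim monitoring. The interim likelihood relies on the Hypothesis 1B null and, as written, leaves unused the data that would relax it. For an assumed wild-type rate ratio of 0.80 or 1.25, the interim relative risk is off by about 0.02 at 1,300 + 1,300 and about 0.04 at 1,000 + 2,300; z shifts by about 0.12 and 0.26. The error grows as typing lags.

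Adding the wild-type outcomes and pooling typed patients for prevalence gained information in every split run, about 2–4% under the common-rate model, but does not by itself remove the bias. Arm-specific rates remove it, at a loss of about 3% (1,000/2,300), 14% (500/2,500) or 32% (300/3,000) when typing lags. That is a trade of bias against variance.

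These sizes rest on the assumed splits, w, wild-type rate and rate ratios, and on asymptotic information. Conditional power was computed with the drift term read as inside Φ. Spartan misreads could also separate the two wild-type rates; that route was not quantified, and Section 15.9.4 monitors it.

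It would be wrong to infer that the trial's final result is biased: the Cox analysis in TaqMan-defined carriers (Section 15.5) does not use the assumption.

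**What to change.** In Appendix C:

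1. Add the binomial likelihood of TaqMan-complete wild-type patients in each arm.
2. Estimate LOF prevalence from all typed patients, not only those in the genotyping arm.
3. At each look, report a version with separate wild-type rates by arm beside the common-rate version. Give the estimate, standard error, information time and conditional power for both, with the numbers of complete and incomplete patients.
4. State before the next look which version is compared with the stopping criteria, and tell the DSMB that the arm-specific version is less precise when typing lags.

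The cost is a few lines of code and revised Appendix C wording. No new data are needed, and the final analysis is unchanged.

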Based on data from Mega and Schuldiner, a hazard ratio as low as 0.60 for ticagrelor versus clopidogrel in reduced function allele carriers may be expected. We intend to power the study to detect a hazard ratio of 0.65 or smaller. This will

require a total of 1,694 patients with reduction function alleles to be randomized, and thus 5,270 patients will be enrolled.

**Table 3.** Required sample size for 80% power

	Minimum detectable effect, hazard ratio		
	0.60	0.65	0.70
Number with reduction function allele required	1,241	1,694	2,401
Number with reduced function to enroll assuming 5% drop out	1,307	1,784	2,528
Number with reduced function allele enrolled at South Korean sites	508	508	508
Number with reduced function allele to enroll at non-Korean sites	799	1,276	2,020
Total number enrolled at Korean sites, assuming 50% prevalence	1,015	1,015	1,015
Total number to enroll at non-Korean sites, assuming 30% prevalence	2,665	4,255	6,734
Total number enrolled	3,680	5,270	7,749

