### 15.2.2 Revised Sample Size Calculations

At the time of this protocol revision (Version 8), the estimated event rate for the primary endpoint across all LOF subjects is 4.8%, substantially lower than the assumptions made in Section 15.2.1. We propose performing updated power calculations using a revised minimum detectable effect of a hazard ratio of 0.50. This effect size is justified by several arguments. First, ticagrelor has already been shown to reduce MACE events by about 16% in all ACS patients, regardless of genotype, in the PLATO trial. However, because our study treatment represents a precision medicine, pharmacogenomic approach, we expect a much greater treatment effect in the targeted LOF population. Second, such effect sizes have been seen in other studies involving CYP2C19 \*2 and \*3 alleles(2,40). Third, a meta-regression analysis of studies comparing event rates in (primarily) clopidogrel-treated patients who were LOF vs. WT suggested an inverse relationship between the overall event rate and the WT vs. LOF advantage, such that the predicted HR

in very low event rates was consistent with 0.50. Finally, at low event rates, a large effect must exist within the LOF population in order to achieve reasonable number-needed-to- treat (NNT) values, since the genotype-guided dual antiplatelet treatment is expected to have no effect in the WT population. For example, if the event rate is 4% in LOF subjects on clopidogrel, and 2% in LOF subjects on ticagrelor, that 50% reduction would equate to a NNT of 50 subjects within the LOF sub-population. If the prevalence of LOF alleles is 30% in the overall population, that would equate to an NNT of 167. Under initial assumptions, the NNT in the LOF sub-population would have been 25 subjects, equating to an overall NNT of 75. Thus, from the perspective of NNT, we are powered to detect a smaller effect than under initial assumptions.

Additional assumptions play a role in the power calculations. First, we assume that around the total enrollment mark of 3900 subjects, 20% of subjects enrolled from

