that point forward will be from Korea. This is lower than observed so far (30%), due to the impending activation of additional sites in North America. Increasing this percentage would result in a smaller required sample size, as it would increase the prevalence of LOF subjects in the study. We also assume that the current prevalence of LOF carriers will continue in Korean (59%) and North American (28%) subjects. Increasing either of these prevalences would reduce the number of subjects required. The power calculations are based on a two-sided log-rank test at a Type I error rate of 0.05 with an expected randomization ratio of 1:1. Table 3 demonstrates the calculations for total subjects enrolled assuming an event rate of 4.5%. Table 4 gives required sample sizes for varying event rates and power levels. These tables show that the previous planned sample size of 5270 subjects provides at least 80% power if the event rate is at least 4.0%.

**Table 4.** Revised Sample Sizes for a Minimum Detectable Hazard Ratio of 0.50 with an overall event rate of 4.5%

	80% Power	85% Power	90% Power
N of LOF subjects required	1560	1784	2086
N of LOF subjects accounting for 5% dropout	1643	1878	2196
N of LOF patients expected from Korea	747	828	937
N of LOF patients expected from North America	896	1050	1259
Total patients expected from Korea	1275	1413	1599
Total patients expected from North America	3192	3742	4486
Total number of patients to enroll	4467	5155	6085

**Table 5.** Required Sample Sizes for a Minimum Detectable Hazard Ratio of 0.50 at varying event rates and power assumptions

Baseline event rate	Power at n=5270	Sample size needed for given power		
		80%	85%	90%
5.0%	89.3%	3955	4570	5409
4.5%	85.8%	4467	5155	6085
4.0%	81.6%	5052	5827	6875

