## 15.8 Monitoring for Futility and Efficacy

Both efficacy and futility monitoring require three estimates: 1) a best current estimate of the treatment effect, as well as 2) uncertainty of the estimate (standard error and/or confidence interval), and 3) an estimate of what proportion of the study's final information is currently in hand, that is, the current value of "information time".

Information time is critical both in assessing conditional power (futility) as well as in doing interim testing using group sequential approaches. Appendix C details how to

construct a combined likelihood combining the information from the complete and the incomplete subject data, which produces the first two required estimates, using likelihood calculations, and specifically, using the profile likelihood method to get down to the one-dimensional likelihood for the treatment effect parameter.

Appendix C also details how to estimate information time (the third required measure). Once we have a current z-score (effect divided by standard error) for the treatment effect, as well as our current estimate of information time, we can then do standard calculations for conditional power (futility) and efficacy

**Futility Monitoring:** We propose that this assessment be based on our calculation of conditional power, as described in Appendix C. In addition to the conditional power calculation, we will provide the modified unconditional power calculation based on current estimates of event rates and the estimate and 95% CI of the average event rate in LOF subjects. We specifically propose that at the time of DSMB reviews, that consideration be given to stopping the trial if the ratio of conditional power to initial power falls below the proportion of remaining information time. For example, if the initial power is 85%, and the proportion of remaining information time is 40%, then the conditional power should exceed 34% ( $0.85 \times 0.4$ ). The basis for the moving target of conditional power is the “sunk cost” argument. The initial study design is assumed to equate the expected utility of a positive result with the cost of the entire study. By equating the ratio between conditional power and initial power, the cost-benefit ratio is maintained. This means that the bar for conditional power for continuing gets progressively lower, as more of the total study costs become a “sunk cost.”

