where  $t$  is information time,  $Z_t$  is the current z-score,  $\Phi$  is the cumulative Gaussian distribution function,  $\Phi^{-1}$  is its inverse and  $P_0$  is the unconditional study power under initial study assumptions.  $Z_t$  will be calculated from the log of the estimated effect and its estimated standard error.

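### In the conditional-power formula of Appendix C the drift term stands outside Φ[...], so the result is negative at 40%, 60% and 80% information whatever the data; confirm the bracket against the PDF and correct it.

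*Combined protocol and SAP*

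**What the plan says.** Appendix C gives one formula for conditional power. As it reads in the extracted text, it is

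CP = 1 − Φ[(Φ⁻¹(0.975) − Z√t)/√(1−t)] − (Φ⁻¹(0.975) + Φ⁻¹(P0)) × √(1−t),

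with the square bracket of Φ closed after the fraction. The last term, "\Phi^{-1}(0.975) + \Phi^{-1}(P_0)) * \sqrt{(1-t", is the drift term. P0 "is the unconditional study power under initial study assumptions". Just before the formula, the appendix states the drift constant: "Our expected power of 85.8% implies that our expected z-score at the end of the trial is 3.031".

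Section 15.8 refers to this calculation for futility. At DSMB reviews, stopping is to be considered if CP divided by the initial power is below the fraction of information still to come, that is, if CP < P0 × (1−t). Its worked example takes 85% power and 40% of information remaining, "then the conditional power should exceed 34" percent. The same section sets efficacy looks at about 40%, 60% and 80% information, with a critical value of 3.291.

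**The concern.** A conditional power is a probability. In the formula as it reads, a quantity well above 1 at the planned information times is subtracted from a number between 0 and 1. The result is negative and cannot be compared with a threshold such as 34%. This is the only formula the plan gives for the futility criterion. If it were programmed literally, the criterion would be met whether the interim result was null, favourable or already past the efficacy boundary. If the programmer repaired it silently, the calculation shown to the DSMB would differ from the documented one with no record of the change.

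**Working it through.** **Inputs.** Two-sided α = 0.05, so Φ⁻¹(0.975) = 1.960 (Section 15.2.2: "two-sided log-rank test at a Type I error rate of 0.05"). Minimum detectable hazard ratio 0.50 (Section 15.2.2). P0 = 0.858 (Appendix C and Table 5) or 0.80 (Section 15.2.1, Table 3: "Required sample size for 80% power"). Both are carried because the definition of P0 refers to initial assumptions, while the appendix works with 85.8%. Information times are 0.4, 0.6 and 0.8 (Section 15.8).

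**The plan's own figures reproduce.** 1.960 + Φ⁻¹(0.858) = 3.0313, against 3.031 stated. ln 2 / 3.0313 = 0.2287 and 1/0.2287² = 19.1, both as stated. 0.85 × 0.40 = 0.34, as in the example. The drift constant is therefore right, and only its position is in question.

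**Formula as it reads.** Since 1 − Φ[...] cannot exceed 1, the ceiling over all Z of either sign is 1 − c√(1−t), with c = 3.0313 for P0 = 0.858 and c = 1.960 + 0.842 = 2.8016 for P0 = 0.80.

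| P0 | t | Drift term | Ceiling of CP | CP at Z = 3.291 | Threshold P0(1−t) |
|---|---|---|---|---|---|
| 0.858 | 0.4 | 2.348 | −1.348 | −1.786 | 0.515 |
| 0.858 | 0.6 | 1.917 | −0.917 | −1.093 | 0.343 |
| 0.858 | 0.8 | 1.356 | −0.356 | −0.370 | 0.172 |
| 0.80 | 0.4 | 2.170 | −1.170 | −1.608 | 0.480 |
| 0.80 | 0.6 | 1.772 | −0.772 | −0.948 | 0.320 |
| 0.80 | 0.8 | 1.253 | −0.253 | −0.267 | 0.160 |

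CP is negative at all three times for any P0 above Φ(1/√0.2 − 1.960) = 0.61.

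**When it could pass.** The ceiling reaches zero at t = 1 − 1/c², which is 0.891 (P0 = 0.858) or 0.873 (P0 = 0.80). It reaches the threshold where 1 − c√(1−t) = P0(1−t), which is t = 0.908 or 0.893.

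**Which form is meant.** At t = 0, CP must equal P0. As it reads, with P0 = 0.858, the formula gives 1 − Φ(1.960) − 3.031 = 0.025 − 3.031 = −3.006. With the drift inside the bracket it gives 1 − Φ(1.960 − 3.0313) = Φ(1.0713) = 0.858 = P0.

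**Formula with the bracket moved** (P0 = 0.858, benefit taken as positive Z):

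| t | CP at Z = 0 | CP at Z = 1 | CP at Z = 1.96 | Threshold | Criterion met below Z of about |
|---|---|---|---|---|---|
| 0.4 | 0.428 | 0.737 | 0.922 | 0.515 | 0.27 |
| 0.6 | 0.119 | 0.517 | 0.889 | 0.343 | 0.64 |
| 0.8 | 0.001 | 0.152 | 0.814 | 0.172 | 1.04 |

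In simulated Brownian paths with reviews at these three times, drift 0 for HR 1 and 3.031 for HR 0.50, the moved-bracket criterion is met by the third review in about 88% and 9% of trials respectively. The criterion then depends on the data.

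**The case against.** The strongest reply is that the plan may contain no error. The point rests on one closing bracket in a displayed equation known only from text extracted from the PDF. A bracket closed too early after a stacked fraction is a plausible extraction fault, and the equation appears only once, so nothing else corroborates it. This stands. If the source closes the bracket after the drift term, the point falls away.

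A second reply is that the slip would be typographical. The drift constant is stated correctly, the 34% example shows that CP is a probability, and a program returning a power near −2 would be questioned at its first run. This also stands, and nothing in the documents indicates that the literal form was ever programmed.

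A reader might infer that the futility rule orders the trial to stop whatever the data show, or that monitoring could not tell a working drug from an inactive one. The documents do not support that. Section 15.8 asks only that stopping be considered. It also supplies a modified unconditional power and the event rate in reduced-function carriers with its 95% CI. Under Appendix G the DSMB advises the Steering Committee. The 40%, 60% and 80% looks are set for efficacy, whereas futility is assessed at DSMB reviews, and beyond about t = 0.91 even the literal formula can pass.

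These replies limit the consequence. They do not make the formula, as it reads, correct.

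**Conclusion.** Subject to the source check, the formula is wrong as it reads and should be corrected. With the drift outside Φ[...], CP is at most −1.35, −0.92 and −0.36 at t = 0.4, 0.6 and 0.8 for P0 = 0.858, and at most −1.17, −0.77 and −0.25 for P0 = 0.80. Taken literally, the advisory criterion is met at every DSMB review before about t = 0.89 (P0 = 0.80) or 0.91 (P0 = 0.858), even with Z at the efficacy boundary. This is more than clerical because the formula drives a stated decision criterion. It is not grave, because the intended form is evident and a literal coding would probably be caught. The result holds for either P0 and either sign of Z. The 88% and 9% figures assume P0 = 0.858, reviews at exactly those three information times, and benefit counted as positive.

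**What to change.** First check the bracket in the source PDF. If it closes after the fraction there too, change Appendix C to

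CP = 1 − Φ[(Φ⁻¹(0.975) − Z√t)/√(1−t) − (Φ⁻¹(0.975) + Φ⁻¹(P0)) × √(1−t)].

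State whether P0 is 0.858 (revised assumptions) or 0.80 (original design), and use the same value in the threshold of Section 15.8. State also that benefit counts as positive Z: Appendix C derives Z from the log of the effect, which is negative when the hazard ratio is below 1, and gives no sign convention.

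Add check values for the DSMB program at t = 0.4:

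| P0 | CP at Z = 0 | CP at Z = 2 |
|---|---|---|
| 0.858 | 0.43 | 0.93 |
| 0.80 | 0.36 | 0.90 |

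The non-zero Z is needed because a check at Z = 0 alone does not test the sign or scaling of the Z term. The cost is one corrected line, two short statements and a small table in Appendix C. Sample size, efficacy boundary and data collection are unaffected.
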